8.1.2.1. Win Ratio

The win ratio analysis is intended to assess whether there is a difference between OCA and placebo in the hierarchical event endpoint (as defined in [Section 2.1.1](#)) while considering the clinical importance order and relative timing of its components.

In the win ratio analysis, two-sided hypotheses are expressed in terms of:

- The null hypotheses (H_0) that the win ratio $R_w = 1$.
- The alternative hypothesis (H_1) that the win ratio $R_w \neq 1$.

The 2 treatment groups will be compared using the win ratio ([Pocock 2012](#)) using the unmatched method within the bilirubin randomization strata. The win ratio represents the odds of having a more favorable outcome versus a less favorable outcome when assigned to the OCA treatment group compared to the placebo treatment group. If the estimated win ratio is greater than 1 then treatment with OCA is considered to be more favorable than treatment with placebo.

8.1.2.1.1. Calculation of the Win Ratio

The components of the composite endpoint are prioritized as follows:

Group 1:

1	
 • Death (all-cause)
2	
 • Liver transplant
3	
 • Hospitalization (as defined by a stay of 24 hours or greater) for new onset or recurrence of: 
 – Variceal bleed – Hepatic encephalopathy (as defined by a West Haven score of ≥ 2) – Spontaneous bacterial peritonitis (confirmed by diagnostic paracentesis OR presence of $>250/\text{mm}^3$ PMNs in the ascitic fluid) – Bacterial empyema (confirmed by diagnostic thoracentesis OR presence of $>250/\text{mm}^3$ PMNs in the pleural fluid)
4	
 • Uncontrolled or refractory ascites (requiring large volume paracentesis)
5	
 • Portal hypertension syndromes: 
 – Hepatorenal syndrome – Portopulmonary syndrome – Hepatopulmonary syndrome
6.1	
 • MELD-Na score ≥ 15 when both subjects have a baseline MELD-Na score < 12
6.2	
 • MELD score ≥ 15 when one or more subjects have a baseline MELD-Na score ≥ 12

Within each baseline bilirubin strata, $k \in (1, 2)$, each subject in the treatment group will be compared to each subject in the placebo group. For each pair, the time to the most important

event (eg, all-cause death) determines the “winner.” If this comparison is non-informative, then the time to the second-most important event (eg, liver transplant) is compared to determine a “winner,” and so on.

For each composite endpoint c , each subject i has (T_{ic}, C_{ic}) , a time of the event and time of censoring (only one observed).

When comparing treated subject t to placebo subject p on time-to-event c ,

- The treated subject “wins” if
 - $(T_{tc}, C_{tc}) > T_{pc}$
- The treated subject “loses” if
 - $T_{tc} < (T_{pc}, C_{pc})$
- The comparison is considered non-informative if
 - neither subject has event c ,
 - $\min(C_{tc}, C_{pc}) < \min(T_{tc}, T_{pc})$, or
 - $T_{tc} = T_{pc}$.

For pairs in which all priority-ranked endpoints are non-informative, the win/loss will be determined as follows:

1. Progression to decompensated liver disease if neither subject has decompensation at baseline. (Group 2)
2. If tiebreaker #1 is non-informative or not applicable: Progression to clinical evidence of portal hypertension without decompensation if neither patient has decompensation or clinical evidence of portal hypertension at baseline. (Group 3)

Tiebreaker #1: progression to decompensated liver disease (for pairs in which both subjects do not have decompensation at baseline):

The components of progression to decompensated liver disease are prioritized as follows (Group 2):

1	
 • New onset of: 
 – Hepatic hydrothorax – Variceal bleeding – Ascites requiring treatment with sodium restriction, diet modification, or diuretics
2	
 • Hepatic encephalopathy requiring lactulose/or rifaximin
3	
 • New onset of Child-Pugh ≥ 7 • New onset of total bilirubin > 3 mg/dL

For each pair, the time to the subjects’ first event from the first priority category determines the “winner.” If this comparison is non-informative, then the time to first occurrence of Child-Pugh ≥ 7 and/or total bilirubin >3 mg/dL is compared to determine a “winner”.

Tiebreaker #2: progression to clinical evidence of portal hypertension without decompensation (for pairs in which both subjects do not have decompensation or clinical evidence of portal hypertension at baseline):

The components of progression to clinical evidence of portal hypertension are prioritized as follows (Group 3):

1	
 • Endoscopic evidence of portal hypertension without bleeding 
 – Gastroesophageal varices (requiring banding or progression to large varices if no or small varices were observed at baseline) – Portal hypertensive gastropathy
2	
 • Platelets $<150 \times 10^9/L$ with splenomegaly and/or with transient elastography >15 kPa

Once all pairs of OCA and placebo-treated subjects are classified as a win or loss for the treatment group (or as non-informative, if none of the tiebreakers determine a winner), the win ratio will be determined.

The win ratio is the total number of wins for the OCA-treated group divided by the total number of losses for the OCA-treated group: $R_w = N_w/N_l$. The 95% confidence interval will be calculated using a bootstrapping method and a p-value will be calculated using the stratified Finkelstein-Schoenfeld test (Finkelstein 1999).

The number and percentage of pairs resulting in wins and losses will be presented by component of the composite endpoint determining the win or loss, by baseline bilirubin strata and overall. The number and percentage of pairs resulting in ties will be presented by baseline bilirubin strata and overall.

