2.1.1. Primary Objective

The primary objective of this study is to compare the effect of obeticholic acid (OCA) to placebo, in conjunction with established local standard of care, on clinical outcomes in subjects with primary biliary cholangitis (PBC) as measured by time to first occurrence of the following adjudicated events, derived as a composite event endpoint (including all Group 1 – Group 3 events).

Group 1:

- Death (all-cause)
- Liver transplant
- Hospitalization (as defined by a stay of 24 hours or greater) for new onset or recurrence of:
 - Variceal bleed
 - Hepatic encephalopathy (as defined by a West Haven score of ≥ 2)
 - Spontaneous bacterial peritonitis (confirmed by diagnostic paracentesis OR presence of $>250/\text{mm}^3$ polymorph leucocytes [PMNs] in the ascitic fluid)
 - Bacterial empyema (confirmed by diagnostic thoracentesis OR presence of $>250/\text{mm}^3$ PMNs in the pleural fluid)
- Uncontrolled or refractory ascites (requiring large volume paracentesis)
- Portal hypertension syndromes:
 - Hepatorenal syndrome (as defined by International Ascites Club [[Angeli 2019](#)])
 - Portopulmonary syndrome
 - Hepatopulmonary syndrome

- Model of end-stage liver disease (MELD)-Na score ≥ 15 if MELD-Na < 12 at baseline
- MELD score ≥ 15 if MELD-Na ≥ 12 at baseline

Group 2:

- Progression to decompensated liver disease (for subjects without decompensation at baseline), prioritized as follows:
 - New onset of:
 - Hepatic hydrothorax
 - Variceal bleeding
 - Ascites requiring treatment with sodium restriction, diet modification, or diuretics
 - Hepatic encephalopathy requiring lactulose and/or rifaximin
 - New onset of:
 - Child-Pugh ≥ 7
 - Total bilirubin > 3 mg/dL

Group 3:

- Progression to clinical evidence of portal hypertension without decompensation (for subjects without decompensation or clinical evidence of portal hypertension at baseline)
 - Endoscopic evidence of portal hypertension without bleeding
 - Gastroesophageal varices (requiring banding or progression to large varices if no or small varices were observed at baseline)
 - Portal hypertensive gastropathy
 - Platelets $< 150 \times 10^9/L$ with splenomegaly and/or with transient elastography > 15 kPa

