14. DEVIATIONS FROM PROTOCOL

14.1. Primary Efficacy Endpoint and Analysis

Due in part to high discontinuation rates and requests from sites to close, the decision was made to stop 747-302 early, at approximately 67% information (84 adjudicated Protocol Version 6 endpoints observed). To increase the number of endpoint events and power to detect a difference, the primary efficacy endpoint has been expanded to include:

- Portal hypertension syndromes (hepatorenal, portopulmonary, or hepatopulmonary)
- Progression to decompensated liver disease (for subjects without decompensation at baseline)
- Progression to clinical evidence of portal hypertension without decompensation (for subjects without decompensation or clinical evidence of portal hypertension at baseline).

The primary efficacy analysis remains the stratified log rank test. With the inclusion of additional endpoints that occur earlier in the course of the disease, the log rank test is limited to each subject's first event, which is likely to be an outcome of lesser clinical importance. A win ratio analysis was added as a sensitivity analysis, to allow for a hierarchical comparison of the composite endpoints. The win ratio analysis allows for the comparison of more severe events such as death and liver transplant to be prioritized over the comparison of earlier-stage events such as progression to clinical evidence of portal hypertension.

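### The rank of hepatic encephalopathy among the Group 2 win-ratio tiebreakers is stated inconsistently, and the two-step text, read with its own table, skips it

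*SAP*

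**What the plan says.** Section 14.1 gives the role of the method: "A win ratio analysis was added as a sensitivity analysis, to allow for a hierarchical comparison of the composite endpoints". Section 8.1.2.1 opens with "The win ratio analysis is intended to assess whether there is a difference between OCA and placebo in the hierarchical event endpoint" and refers to Section 2.1.1 for its definition.

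Three places then bear on the order inside Group 2.

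- **Section 2.1.1, Group 2.** The list is itself a ranking: "Progression to decompensated liver disease (for subjects without decompensation at baseline), prioritized as follows". Two new-onset blocks follow. The first holds hydrothorax, variceal bleeding, ascites and "Hepatic encephalopathy requiring lactulose and/or rifaximin". The second holds Child-Pugh ≥7 and total bilirubin >3 mg/dL.
- **Section 8.1.2.1.1, Tiebreaker #1 table.** Three numbered rows. Row 1 is hydrothorax, variceal bleeding and ascites. Row 2 is "Hepatic encephalopathy requiring lactulose/or rifaximin", alone. Row 3 is Child-Pugh and bilirubin.
- **Section 8.1.2.1.1, text under that table.** Two steps. The time to each subject's "first event from the first priority category determines the" winner. The next sentence begins "If this comparison is non-informative, then the time to first occurrence of Child-Pugh" and adds bilirubin. There is no third step.

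The estimand table in Section 8.1 refers to Sections 2.1.1 and 8.1.1 for the prioritisation. Section 8.1.1 contains no priority list, so it does not settle the matter.

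**The concern.** A win ratio is defined by its ordered list of comparisons. If the list differs between sections, the programmer chooses the estimator. Here the uncertain element is a clinical decompensation event, and the step that would replace it is a score or laboratory threshold. A pair in which one subject needed treatment for encephalopathy could be decided by the other subject's bilirubin, or left tied, depending on which sentence is coded.

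The same pairwise scores feed the win ratio and the breakdown of wins and losses by component (Section 8.1.2.1.1), the bootstrap interval (8.1.2.1.2) and the Finkelstein-Schoenfeld statistic (8.1.2.1.3). An inconsistency in the rule therefore reaches all of these.

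**Working it through.** The plan gives no figure for this point, so there is none to reproduce. The check writes the possible orders out as pairwise rules and applies them to the same pairs.

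**Rules**

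- R1, Section 2.1.1: {hydrothorax, variceal bleeding, ascites, encephalopathy}, then {Child-Pugh, bilirubin}.
- R2, the table row by row: {hydrothorax, variceal bleeding, ascites}, then {encephalopathy}, then {Child-Pugh, bilirubin}.
- R3, the two-step text with the table's row 1 as its first category: {hydrothorax, variceal bleeding, ascites}, then {Child-Pugh, bilirubin}.

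The two-step text read with the first block of Section 2.1.1 is identical to R1.

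**Comparison at each level (Section 8.1.2.1.1).** The OCA subject wins if the placebo subject's event comes before the OCA subject's event or censoring. The OCA subject loses in the reverse case. Otherwise the next level is used.

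**Assumed pairs.** Both subjects are free of decompensation at baseline, have no Group 1 events and no events other than those shown, and are followed to day 1500.

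| Pair | R1 | R2 | R3 |
|---|---|---|---|
| A: OCA encephalopathy day 400; placebo no event | OCA loss | OCA loss | non-informative |
| B: OCA encephalopathy day 400; placebo bilirubin >3 mg/dL day 300 | OCA loss | OCA loss | OCA win |
| C: OCA ascites day 900; placebo encephalopathy day 400 | OCA win | OCA loss | OCA loss |

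**Steps**

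- Pair A. R1 level 1 and R2 level 2 compare day 400 with censoring at day 1500: OCA loss. R3 finds no event at either step, so the pair passes to Tiebreaker #2, where there is also nothing to compare.
- Pair B. R1 and R2 reach encephalopathy before bilirubin: 400 < 1500, OCA loss. R3 skips encephalopathy and compares bilirubin: the placebo event on day 300 precedes OCA censoring on day 1500, OCA win.
- Pair C. R1 has both events in one level: the placebo event on day 400 precedes the OCA event on day 900, OCA win. R2 and R3 find only the OCA ascites in row 1: 900 < 1500, OCA loss.

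Pairs A and B show the effect of the step missing from the text. Pair C shows that the table and Section 2.1.1 disagree even when every row is compared. Adding a sentence for row 2 without changing Section 2.1.1 would therefore leave a conflict.

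**The case against.** The strongest reply is that the text and Section 2.1.1 agree. Read alone, the two-step text matches the two levels of Section 2.1.1, and Section 8.1.2.1 names that section as the definition. On this view the table's row 2 is a slip and encephalopathy is compared at step 1. This is plausible, and it is why the simplest repair changes the table. It does not remove the problem: the text stands directly below a table with numbered rows, and its first priority category naturally means row 1 of that table.

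A reader might infer more than the document supports:

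- **That encephalopathy is never compared in the win ratio.** It would be missed only if the text is combined with the table, and only in Tiebreaker #1. Under Section 2.1.1, or under the general rule in Section 8.1.2.1.1 of moving on to the next most important event, it is compared. On every reading, hospitalisation for "Hepatic encephalopathy (as defined by a West Haven score of ≥ 2") is compared in Group 1, priority 3.
- **That the text contradicts Section 2.1.1.** It does not. The table differs from Section 2.1.1, and the text lacks a step for the table's row 2.
- **That the purpose in Section 14.1 is defeated.** The examples there are death and transplant ranked above progression to portal hypertension. That order is untouched.
- **That a count of affected pairs can be given.** The Clinical Pharmacology Analysis Plan reports about 334 subjects enrolled with 1:1 allocation, about 167 per arm. The SAP gives neither the split by bilirubin stratum, nor the number decompensated at baseline, nor the number with encephalopathy. Any count would rest on invented inputs. Pairs decided in Group 1, pairs with baseline decompensation in either subject, and pairs in which all readings agree do not change.

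The reporting of wins and losses by component would reveal how encephalopathy was handled, but only once the results are known.

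**Conclusion.** The inconsistency is real and should be corrected. The document supports at least two complete orders for Group 2, and a third that omits a clinical event, and the same pair can be a win, a loss or a tie according to the one used.

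Its reach is narrow. It concerns sensitivity analysis 2 in Section 8.1.2, and within that only pairs that reach Tiebreaker #1. The primary stratified log rank test takes the first event from any group, so the order inside Group 2 cannot change it. The win ratio is not part of the key secondary testing sequence in Sections 8.2 and 8.6, and Section 8.2 excludes it for the endpoint that is primary in the EMA filing. The size of the effect on the win ratio cannot be estimated from the document.

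The conclusion assumes that encephalopathy belongs to the first new-onset block of Section 2.1.1, as its place in the list indicates. If the page layout sets it apart as a level of its own, Section 2.1.1 would agree with the table. The missing step in the text would still need correcting.

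**What to change.** Before unblinding, state one Group 2 order in Section 2.1.1, in the Tiebreaker #1 table and in the text below it, with one comparison step per level.

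- Simplest: move encephalopathy into row 1 of the table with the wording of Section 2.1.1, renumber Child-Pugh and bilirubin as row 2, and keep the two-step text.
- If three levels are intended: add the encephalopathy step to the text and change Section 2.1.1 to three levels.

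In either case, correct the estimand table's reference to Section 8.1.1 so that it points to Section 8.1.2.1.1, where the list stands. The cost is a few words in the SAP and one line of the pairwise algorithm. No new data are needed and no other analysis changes.

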8.1.2.1.2. Calculation of the (1- α)% confidence interval

In the bootstrap method, the original data is sampled with replacement a large number of times, the win ratio is calculated for each sample, and an empirical distribution of the win ratio is determined from the total number of samples. Because the distribution of the win ratio is skewed, the (1- α)% CI for the population win ratio will be calculated by application of a bias-corrected method on the log-transformed win ratio, as recommended by Wang and Pocock (2016). The null hypothesis H_0 will be rejected in favor of the alternative H_a at the α % significant level if the (1- α)% CI does not contain 1.

The bootstrap method proceeds as follows:

Step 1: Within each baseline bilirubin strata, draw a random sample S_{Placebo} of size N_{Placebo} with replacement from the original placebo treatment group in the ITT population and a random sample S_{OCA} of N_{OCA} with replacement from original OCA treatment group in the ITT

population, where N_{Placebo} and N_{OCA} are the total number of placebo and OCA patients in the ITT population, respectively.

Step 2: Perform the win ratio analysis on the sample (S_{Placebo} , S_{OCA}) and calculate the log win ratio (log R_w).

Step 3: Repeat steps 1 and 2 M times, where M is 5,000.

Step 4: Obtain $(1-\alpha)\%$ CI for log R_w using the bias correction and acceleration (BCa) method and exponentiate these percentiles: these are the estimated limits of the $(1-\alpha)\%$ CI for the win ratio.

8.1.2.1.3. Calculation of the Finkelstein-Schoenfeld Test Statistic

The stratified Finkelstein-Schoenfeld test is a generalization of the Gehan-Wilcoxon test which compares each pair of subjects i and j within strata k using a score:

$$u_{ij} \begin{cases} 1, & \text{if } i \text{ does "better than" } j \\ -1, & \text{if } i \text{ does "worse than" } j \\ 0, & \text{if it is indeterminate,} \end{cases}$$

where $i, j = 1, \dots, n_k$, with $i \neq j$ and n_k is the total number of subjects in the strata k . All subjects are compared pairwise with wins, loses, and ties determined as described in [Section 8.1.2.1.1](#).

The “rank” for subject i is $U_i = \sum_{j \in A_k} u_{ij}$, where A_k is the set of indices of the n_k subjects in strata k . The test is based on $T = \sum_k \sum_{i \in A_k} U_i D_i$, where $D_i = 1$ for subjects in the treatment group and $D_i = 0$ for subjects in the placebo group, and variance

$$V = \sum_k \frac{m_k(n_k - m_k)}{n_k(n_k - 1)} \left(\sum_{i \in A_k} U_i^2 \right), \text{ where } m_k \text{ is the number of OCA-treated subjects in strata } k.$$

The null hypothesis of this test is that none of the survival nor tiebreaker measures is affected by treatment, and the alternative is that at least one measure is improved in the treatment arm compared to the placebo arm, and is tested by comparing $T/V^{1/2}$ to the normal distribution.

8.2. Key Secondary Efficacy Endpoints

The key secondary efficacy endpoints are as follows:

- To assess the effect of OCA compared to placebo on time to first occurrence of death, liver transplant, MELD-Na score ≥ 15 if MELD-Na < 12 at baseline, MELD score ≥ 15 if MELD-Na ≥ 12 at baseline, uncontrolled or refractory ascites, portal hypertension syndromes (hepatorenal syndrome, portopulmonary syndrome, hepatopulmonary syndrome), or hospitalization for new onset or recurrence of variceal bleed, hepatic encephalopathy, spontaneous bacterial peritonitis, or bacterial empyema.
- Time to first occurrence of death, liver transplant, MELD ≥ 15 , uncontrolled ascites, or hospitalization for new onset or recurrence of variceal bleed, hepatic encephalopathy, or spontaneous bacterial peritonitis. This will be used as the primary endpoint for European Medicines Agency (EMA) filing, and therefore all sensitivity analyses described in [Section 8.1.2](#) will be performed for this endpoint, with the exception of the win ratio analysis. The endpoint described in [Section 8.1](#) will be

considered the first key secondary endpoint for the EMA filing, followed by the remaining key secondary efficacy endpoints described in this section.

- Time to liver transplant or death (all-cause)

8.2.1. Analyses of the Secondary Endpoints

The key secondary efficacy endpoints will compare OCA to placebo using the ITT Population. Data collected after the intercurrent events will be included (the treatment policy). Only adjudicated events will be included in the time-to-event analyses.

The time-to-event secondary efficacy analyses will compare OCA to placebo with respect to the secondary efficacy endpoints using the ITT Population. Only adjudicated events will be included in the time-to-event analyses. Time-to-event secondary efficacy analyses will use the same methodology as specified for the primary efficacy endpoint ([Section 8.1.1](#)).

8.2.2. Sensitivity Analyses

The following sensitivity analyses will be carried out on the key secondary endpoints.

1. For key secondary time-to-event endpoints, the same analyses will be performed for PP population. Data collected after the intercurrent events will be included (treatment policy). No KM plot will be generated.

8.3. Additional Secondary Efficacy Endpoints

8.3.1. Time to Event Analyses

The following time-to-event secondary efficacy analyses will compare OCA versus placebo using the ITT population:

- Time to each relevant component of the primary efficacy endpoint
- Time to development of varix/varices
- Progression to cirrhosis
- Time to occurrence of HCC
- Time to liver-related death
- Time to liver-related death or liver transplant
- Time to liver-related death, liver transplant, or MELD score ≥ 15

All additional secondary time-to-event outcomes with the exception of death will be analyzed in the context of competing risks.

For the following secondary endpoints, liver transplant and death will be considered competing risks:

- Time to each relevant component of the primary efficacy endpoint, with the exception of death and liver-transplant
- Time to development of varix/varices

- Progression to cirrhosis
- Time to occurrence of HCC

For the following secondary endpoints, death will be considered a competing risk:

- Time to liver-transplant

For the following secondary endpoints, non-liver-related death will be considered a competing risk:

- Time to liver-related death
- Time to liver-related death or liver transplant
- Time to liver-related death, liver transplant, or MELD score ≥ 15

Competing risk outcomes will be compared and summarized through a cumulative incidence function (CIF). Gray's (1988) non-parametric test will be used to compare the CIFs of the two treatment groups. Hazard ratios and their 95% confidence intervals will be computed following the Fine and Gray model (1999). Fine and Gray's hazard model can be fit in SAS version 9.4 and higher by specifying eventcode option in PROC PHREG.

Progression to cirrhosis will be assessed in the subset of subjects considered noncirrhotic at Baseline using available medical history, clinical, and laboratory assessments as well as baseline transient elastography (TE), where available. Specifically, subjects with no clinical, laboratory, or radiological evidence of cirrhosis at baseline and/or a TE liver stiffness of < 16.9 kPa (Corpechot 2012) will be considered noncirrhotic. Progression to cirrhosis will be assessed by the development of clinical, laboratory, or radiological evidence of cirrhosis and/or when liver stiffness increases to ≥ 16.9 kPa during the study in which case histological progression to cirrhosis should be confirmed by biopsy unless not medically indicated.

The percentage of noncirrhotic subjects progressing to cirrhosis during the treatment period will also be summarized by treatment group and compared using a Cochran-Mantel-Haenszel (CMH) test stratified by the randomization stratification factor.

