8.4.4. Liver Histology

A paired biopsy sub-study was recommended by Regulatory Authorities, to further assess clinical outcomes in terms of histological progression to cirrhosis and is described in Protocol Addendum 2. While biopsies were collected, no paired data exists; no analysis will be run.

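### The 'and/or' in the baseline rule for progression to cirrhosis lets subjects with one marker of cirrhosis into the noncirrhotic risk set, so prevalent disease can be counted as incident

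*SAP*

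**What the plan says.** SAP Section 8.3.1 sets the risk set first: "Progression to cirrhosis will be assessed in the subset of subjects considered noncirrhotic at Baseline". Status is to be judged from the available history, clinical and laboratory data, together with baseline transient elastography (TE) where there is a reading. The next sentence makes this operational. Noncirrhotic means "no clinical, laboratory, or radiological evidence of cirrhosis at baseline and/or a TE liver stiffness of < 16.9 kPa".

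The event is defined in two limbs. The first reads: "Progression to cirrhosis will be assessed by the development of clinical, laboratory, or radiological evidence of cirrhosis". The second continues: "and/or when liver stiffness increases to ≥ 16.9 kPa during the study". A qualifier follows, that "histological progression to cirrhosis should be confirmed by biopsy unless not medically indicated".

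The endpoint is compared by Gray's test and the Fine-Gray model, with liver transplant and death as competing risks. In addition, "The percentage of noncirrhotic subjects progressing to cirrhosis during the treatment period will also be summarized by treatment group", with a stratified CMH test.

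On histology, Section 8.4.4 states: "While biopsies were collected, no paired data exists; no analysis will be run".

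**The concern.** If either marker is enough to establish cirrhosis during the study, being free of cirrhosis at baseline requires both to be absent. The complement of an 'or' is an 'and'. The baseline rule also uses an 'or', so a subject can satisfy it on one marker while the other is already positive.

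Such a subject carries prevalent disease by the plan's own event criteria. If the second marker turns positive later, the plan records an incident progression. Events of this kind do not measure what the endpoint is meant to measure, which is passage from no cirrhosis to cirrhosis under treatment. If they occur at a similar rate in both arms, they raise both event rates and pull the comparison towards no difference. Progression to cirrhosis is a listed secondary objective (Section 2.1.2), so its risk set should be unambiguous.

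**Working it through.** The SAP gives no event count, rate or power for this endpoint, so there is no stated figure to reproduce. The check is one of logic, followed by an illustration on assumed inputs.

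**Step 1: list the baseline states.** There are two levels of clinical, laboratory or radiological evidence and three of TE, giving six states. Three rules are applied to each:
- as written: noncirrhotic if (no evidence) or (TE < 16.9 kPa);
- marker positive: (evidence) or (TE ≥ 16.9 kPa), the markers used for progression;
- corrected: noncirrhotic if (no evidence) and, where TE is available, (TE < 16.9 kPa).

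| Evidence | Baseline TE | As written | A marker already positive | Corrected |
|---|---|---|---|---|
| no | < 16.9 | noncirrhotic | no | noncirrhotic |
| no | ≥ 16.9 | **noncirrhotic** | **yes** | excluded |
| no | none | noncirrhotic | no | noncirrhotic |
| yes | < 16.9 | **noncirrhotic** | **yes** | excluded |
| yes | ≥ 16.9 | excluded | yes | excluded |
| yes | none | excluded | yes | excluded |

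As written, 2 of the 6 states are in the risk set with a marker already positive. Under the corrected rule, 0 of 6 are, and subjects with no evidence and no TE stay eligible.

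**Step 2: how these two states become events.** Both event limbs describe a change, so a repeat of the baseline finding is not an event on a plain reading. The route is the other marker:
- no evidence, TE ≥ 16.9 kPa at baseline: an event when clinical, laboratory or radiological evidence is first recorded;
- evidence present, TE < 16.9 kPa at baseline: an event when TE later reaches 16.9 kPa.

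No rule in the SAP excludes an event in a subject who already met the other limb at baseline. The biopsy request can be waived. One on-study biopsy does not date the onset of cirrhosis, and there are no paired biopsies that could.

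**Step 3: size, on assumed inputs.** Let p be the true risk in an arm, m the share of the risk set with a marker already positive, and q the share of those who become events, taken as equal in both arms. Then

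observed risk = (1 − m)p + mq.

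When the OCA risk is below the placebo risk, the observed risk ratio rises with q. So q = 1 gives the most dilution for a given m, and q = 0 returns the true ratio on this simplified scale. With assumed risks of 10% on placebo and 6% on OCA (ratio 0.60) and q = 1:
- m = 5%: 0.95 × 0.10 + 0.05 = 14.5%; 0.95 × 0.06 + 0.05 = 10.7%; ratio 0.107/0.145 = 0.74.
- m = 10%: 0.90 × 0.10 + 0.10 = 19.0%; 0.90 × 0.06 + 0.10 = 15.4%; ratio 0.154/0.190 = 0.81.
- m = 20%: 0.80 × 0.10 + 0.20 = 28.0%; 0.80 × 0.06 + 0.20 = 24.8%; ratio 0.248/0.280 = 0.89.

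With assumed risks of 20% and 12% (again 0.60) and q = 1, the ratios are 0.164/0.240 = 0.68, 0.208/0.280 = 0.74 and 0.296/0.360 = 0.82. The upper bound therefore depends on the assumed risks as well as on m.

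**The case against.** The strongest reply is that the event wording protects the endpoint. A reader might infer that a subject at 20 kPa at baseline and 20 kPa at the next scan counts as progressing, or that cirrhosis already seen on imaging meets the radiological limb at the first reassessment. The document does not support that. Evidence must develop and stiffness must increase to the threshold, and an unchanged finding does neither. This part of the objection stands. It limits the concern to conversion on the other marker and makes q = 1 a bound, not an expectation.

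A second reply is that the intent is clear. The preceding sentence combines TE with the other assessments and says it is used where available, so the 'or' was probably meant for subjects without a reading. That is the likely intent. But the sentence that makes the definition operational does not restrict the 'or' in that way, and no other section does. The noncirrhotic category in Appendix A rests on investigator judgement, serves the Child-Pugh classification and does not settle the matter. A programmer could defensibly code either version.

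Third, nothing shows that a subject in a discordant state is truly cirrhotic. TE is a surrogate, and biopsy might be negative. That also stands: the point is only that the subject already meets a marker the plan accepts as sufficient. The biopsy safeguard remains weak for the reasons in the working.

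Finally, the interim SAP (Sections 1, 4.3.3 and 6.2) leaves the method of evaluating progression to cirrhosis to a separate document, which is not at hand. It does so for a blinded review of whether to add this event to the primary endpoint. Section 8.3.1 of the final SAP states its own rule without citing that document. Operational rules may still exist there, so how events were actually counted is uncertain.

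**Conclusion.** The point holds as a defect of definition. Read literally, the baseline rule admits two discordant states in which one sufficient marker is already positive, and later conversion on the other marker would be counted as incident progression. The likely effect is dilution of the Gray, Fine-Gray and CMH comparisons. That direction assumes such conversions are about equally frequent in the two arms.

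The size is unknown, because the document does not give the number of discordant subjects. The ratios of 0.74 to 0.89 are an assumed upper bound on dilution for the 10% and 6% illustration, not an estimate. They are ratios of proportions, so they correspond to the CMH comparison and not directly to the Fine-Gray hazard ratio.

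The consequence is contained. This is an additional secondary endpoint, outside the key secondary hierarchy and tested at a nominal 0.041 level (Section 8.6). Primary and key secondary results are unaffected. The correction is still worth making, because it is cheap and removes an avoidable source of bias.

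**What to change.** In the baseline rule of Section 8.3.1, replace 'and/or' with 'and, where baseline TE is available,'. A subject is then noncirrhotic only with no clinical, laboratory or radiological evidence of cirrhosis and, if TE was measured, a value below 16.9 kPa. Anyone meeting either progression limb at baseline leaves the risk set. Use the same subset for the Gray, Fine-Gray and CMH analyses.

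The cost is one change of wording, the matching change to the derivation, and a slightly smaller risk set. Subjects without a baseline TE and without other evidence are kept.
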